### **5.8.2 Deaths**

Separate summaries for on-treatment and all deaths will be produced by SOC and PT.

All deaths will be listed for the Safety set, post treatment deaths will be flagged. A separate listing of deaths prior to starting treatment will be provided for all screened patients.

### **5.8.3 Laboratory data**

On analyzing laboratory, data from all sources will be combined. The summaries will include all assessments available for the lab parameter collected no later than 30 days after the last study treatment administration date.

The following summaries will be produced for hematology and biochemistry laboratory data (by laboratory parameter and treatment):

- Worst post-baseline CTC grade (regardless of the baseline status). Each subject will be counted only for the worst grade observed post-baseline.
- Shift tables using CTC grades to compare baseline to the worst on-treatment value
- For laboratory tests where CTC grades are not defined, shift tables using the low/normal/high/(low and high) classification to compare baseline to the worst on-treatment value.
- Trends of chemistry and hematology lab parameter values over time should be displayed via boxplots based on time windows and corresponding tables displaying the statistics used for the box plots by the selected time points.

The following listings will be produced for the laboratory data:

- Listings of all laboratory data, with CTC grades and classification relative to the laboratory normal range. Lab data collected during the post-treatment period will be flagged.
- Listing of all CTC grade 3 or 4 laboratory toxicities.

### **Liver parameters**

Liver parameters of interest are total bilirubin (TBL), ALT, AST and alkaline phosphatase (ALP). The number (%) of patients with worst post-baseline values as per Novartis Liver Toxicity guidelines will be summarized:

The following summaries will be produced:

- ALT or AST > 3xULN
- ALT or AST > 5xULN
- ALT or AST > 8xULN

- ALT or AST > 10xULN
- ALT or AST > 20xULN
- TBL > 2xULN
- TBL > 3xULN
- ALT or AST > 3xULN & TBL > 2xULN
- ALT or AST > 3xULN & TBL > 2xULN & ALP < 2xULN (potential Hy's law)

Potential Hy's Law events are defined as those patients with occurrence of AST or ALT > 3xULN and TBL > 2xULN, and ALP < 2xULN at initial presentation during the on-treatment period. Note that the criteria relating to combined elevations of AST (or ALT) and TBL are based on the peak values at any post-baseline time for a patient.

For patients with abnormal ALT or AST baseline values, a clinically significant liver safety signal corresponding to Hy's law is defined by : [ALT or AST > 3\*baseline] OR [ALT or AST > 8\*ULN], whichever is lower, combined with [TBIL > 2\*baseline AND > 2\*ULN].

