5.1 Inclusion criteria

Subjects eligible for inclusion in this study must meet **all** of the following criteria:

1. ≥ 18 years of age
2. Signed informed consent must be obtained prior to participation in the study.
3. Completely resected histologically confirmed cutaneous melanoma stage IIIA (LN metastasis >1 mm), IIIB, IIIC, IIID [AJCC (ed 8) *see appendix 16.1*] no more than 12 weeks, from last surgery, before Day 1
 - a. Subjects presenting with initial resectable lymph node recurrence after a diagnosis of Stage I or II melanoma are eligible.
 - b. Patients who have previously had Stage III melanoma at any time are not eligible
 - c. Recovered from definitive surgery (e.g. no uncontrolled wound infections or indwelling drains).
 - d. Complete nodal resection is not mandatory for microscopic (SNB) disease
 - e. Full therapeutic lymph node dissection (TLND) is required for macroscopic disease, as per established treatment guidelines.
4. V600E/K mutation positive using a validated local test
5. Eastern Cooperative Oncology Group (ECOG) Performance Status of 0-1
6. Subject has adequate bone marrow and organ function as defined by the following laboratory values without continuous supportive treatment (such as blood transfusion, coagulation factors and/or platelet infusion, or red/white blood cell growth factor administration) as assessed by laboratory for eligibility:
 - Hematological
 - Absolute neutrophil count $\geq 1.5 \times 10^9/L$
 - Platelet count $\geq 100 \times 10^9/L$
 - Hemoglobin ≥ 9 g/dL
 - Coagulation
 - PT/INR and PTT $\leq 1.5 \times$ ULN. Subjects receiving anticoagulation treatment may be allowed to participate with INR established within the therapeutic range prior to Day 1
 - Renal
 - Serum creatinine < 1.5 mg/dL
 - Hepatic

- Total bilirubin $\leq 1.5 \times \text{ULN}$ except for subjects with Gilbert's syndrome who may only be included if the total bilirubin is $\leq 3.0 \times \text{ULN}$ or direct bilirubin $\leq 1.5 \times \text{ULN}$
 - Aspartate transaminase (AST) $< 2.5 \times \text{ULN}$
 - Alanine transaminase (ALT) $< 2.5 \times \text{ULN}$
 - Albumin $\geq 2.5 \text{ g/dL}$
7. Left ventricular ejection fraction (LVEF) \geq lower limit of institutional normal (LLN) as assessed by ECHO or MUGA scan
 8. Able to swallow and retain oral medication and must not have any clinically significant gastrointestinal abnormalities that may alter absorption such as malabsorption syndrome or major resection of the stomach or bowels

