6.5.2 Follow-up for toxicities

6.5.2.1 Follow up on potential drug-induced liver injury (DILI) cases

Subjects with transaminase increase combined with total bilirubin (TBIL) increase may be indicative of potential DILI, and should be considered as clinically important events.

The threshold for potential DILI may depend on the subject's baseline AST/ALT and TBIL value; subjects meeting any of the following criteria will require further follow-up as outlined below:

- For subjects with normal ALT and AST and TBIL value at baseline: AST or ALT > 3.0 x ULN combined with TBIL > 2.0 x ULN
- For subjects with elevated AST or ALT or TBIL value at baseline: [AST or ALT > 2 x baseline AND > 3.0 x ULN] OR [AST or ALT > 8.0 x ULN], combined with [TBIL > 2 x baseline AND > 2.0 x ULN]

Medical review needs to ensure that liver test elevations are not caused by cholestasis, defined as ALP elevation > 2.0 x ULN with R value < 2 in subjects without bone metastasis, or elevation of ALP liver fraction in subjects with bone metastasis.

Note: (The R value is calculated by dividing the ALT by the ALP, using multiples of the ULN for both values. It denotes whether the relative pattern of ALT and/or ALP elevation is due to cholestatic ($R \leq 2$), hepatocellular ($R \geq 5$), or mixed ($R > 2$ and < 5) liver injury).

In the absence of cholestasis, these subjects should be immediately discontinued from study drug treatment, and repeat LFT testing as soon as possible, preferably within 48 hours from the awareness of the abnormal results. The evaluation should include laboratory tests, detailed history, physical assessment and the possibility of liver metastasis or new liver lesions, obstructions/compressions, etc.

1. Laboratory tests should include ALT, AST, albumin, creatine kinase, total bilirubin, direct and indirect bilirubin, GGT, prothrombin time (PT)/INR and alkaline phosphatase.
2. A detailed history, including relevant information, such as review of ethanol, concomitant medications, herbal remedies, supplement consumption, history of any pre-existing liver conditions or risk factors, should be collected.
3. Further testing for acute hepatitis A, B, C or E infection and liver imaging (e.g., biliary tract) may be warranted.
4. Additional testing for other hepatotropic viral infection (e.g., CMV, EBV, Adenovirus, HSV, HHV6, HIV), autoimmune hepatitis or liver biopsy may be considered as clinically indicated or after consultation with specialist/hepatologist.

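### The SAP's Hy's law rule ignores raised baseline bilirubin unless ALT or AST is also abnormal, so a subject with stable bilirubin above 2 × ULN can be counted on a transaminase rise alone

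*SAP*

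**What the plan says.** **SAP 5.8.3, Liver parameters.** One planned row counts subjects with ALT or AST above 3 × ULN and TBL above 2 × ULN. The next adds alkaline phosphatase: "ALT or AST > 3xULN & TBL > 2xULN & ALP < 2xULN (potential Hy's law"). Neither row contains a baseline term. On timing, the SAP says: "Note that the criteria relating to combined elevations of AST (or ALT) and TBL are based on the peak values", at any post-baseline time. It then gives an adjusted rule: "For patients with abnormal ALT or AST baseline values, a clinically significant liver safety signal" of the Hy's law kind requires ALT or AST above 3 × baseline or above 8 × ULN, whichever is lower, together with TBL above 2 × baseline and above 2 × ULN.

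**Protocol 6.5.2.1.** The plain thresholds (AST or ALT above 3 × ULN, TBL above 2 × ULN) are for subjects whose ALT, AST and TBL are all normal at baseline. A second rule begins: "For subjects with elevated AST or ALT or TBIL value at baseline". It requires AST or ALT above both 2 × baseline and 3 × ULN, or above 8 × ULN, together with TBL above both 2 × baseline and 2 × ULN.

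**Protocol 5.1, criterion 6.** The general TBL limit is 1.5 × ULN, "except for subjects with Gilbert's syndrome who may only be included if the total bilirubin is" at most 3.0 × ULN, or direct bilirubin at most 1.5 × ULN.

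SAP section 7, on departures from the protocol's analyses, covers COVID-19 and label-update outputs. It does not mention this difference.

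**The concern.** The two documents share the bilirubin condition but trigger it differently: the SAP drops raised baseline bilirubin as a trigger. The subjects left out are those whose baseline bilirubin most needs to be taken into account, and the eligibility criteria knowingly admit them.

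The study report could therefore list subjects under potential Hy's law who never met the protocol's own threshold for potential drug-induced liver injury. Counts in these rows are usually very small, so a single such subject would be noticed and would need explaining. The peak-value convention makes this easier, because the ALT/AST and TBL maxima need not occur together.

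**Working it through.** The plan states no figure on this point, so there is none to reproduce. The check applies the rules as written to a defined subject.

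**Step 1: which rule applies.** Take baseline ALT/AST 0.8 × ULN, ALP 1.0 × ULN and baseline TBL of *b* × ULN, with TBL unchanged throughout. Baseline ALT/AST is normal, so the SAP's adjusted rule does not apply and only the plain rows do. Where *b* is above 1, the protocol's second rule applies, because TBL is elevated.

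**Step 2: who is counted with no rise in bilirubin.**

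| Baseline = peak TBL (× ULN) | Peak ALT (× ULN) | SAP potential Hy's law row | Protocol 6.5.2.1 |
|---|---|---|---|
| 1.0, 1.5, 1.8, 2.0 | 1.0 to 9 | not counted | not flagged |
| 2.1, 2.5, 3.0 | 1.0, 2.9 | not counted | not flagged |
| 2.1, 2.5, 3.0 | 3.5, 6, 9 | **counted** | not flagged |

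The two definitions part only where baseline TBL exceeds 2 × ULN and ALT or AST passes 3 × ULN. The same subjects meet the combined row without the ALP condition.

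**Step 3: bilirubin the protocol requires.** The threshold is the larger of 2 × *b* and 2 (× ULN):
- *b* = 2.1: 2 × 2.1 = 4.2
- *b* = 2.4: 2 × 2.4 = 4.8
- *b* = 2.5: 2 × 2.5 = 5.0
- *b* = 3.0: 2 × 3.0 = 6.0

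The SAP's threshold stays at 2.0 throughout.

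**Step 4: scale, by assumption only.** The enrolled number is 556 (SAP section 6). The documents give no frequency of Gilbert's syndrome, no bilirubin distribution and no rate of ALT/AST above 3 × ULN. Protocol 1.1.1.6 gives 7% above 5 × ULN in COMBI-AD. Assume that 3–10% have Gilbert's syndrome, 5–30% of those have TBL above 2 × ULN, and 7–15% of these reach ALT/AST above 3 × ULN:
- low: 556 × 0.03 × 0.05 × 0.07 = 0.06
- middle: 556 × 0.05 × 0.15 × 0.15 = 0.63
- high: 556 × 0.10 × 0.30 × 0.15 = 2.5

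These products treat the rates as independent and make no reduction for abnormal baseline ALT/AST or for ALP at or above 2 × ULN.

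**Step 5: would widening the SAP trigger be enough?** No. The SAP's adjusted transaminase limb has no 3 × ULN floor. At baseline ALT 0.5 × ULN it is met above 3 × 0.5 = 1.5 × ULN. The protocol's limb needs more than the larger of 2 × 0.5 = 1.0 and 3.0, so 3.0 × ULN. Adding TBL to the trigger alone would correct the bilirubin limb and loosen the transaminase limb.

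**The case against.** The strongest reply is that the row is a broad screen, labelled as potential and tied by the SAP to sponsor liver-toxicity guidelines that are not in these documents. Protocol 6.5.2.1 governs follow-up of individual subjects, and protocol section 12.5.2 defines no Hy's law table, so a different trigger may be deliberate. Individual cases are settled by medical review, repeat testing and a search for other causes. The planned shift tables and full laboratory listings would also show the baseline: TBL of 2.4 × ULN lies in the Grade 2 band of protocol Table 6-7, so an unchanged value shows no shift.

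Part of this stands. The table is descriptive, the study has one arm, and no test or stopping rule uses the count. But a purely plain screen would not explain the SAP's choice: it already adjusts for baseline bilirubin, yet does so on abnormal ALT/AST and not on abnormal bilirubin. Shift tables and listings help a reader diagnose a case without removing it from the row.

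Three stronger readings are not supported:
- A reader might infer that Gilbert's subjects are counted on baseline bilirubin alone. They are not: ALT or AST must also exceed 3 × ULN, and those at or below 2 × ULN are not counted without a rise.
- A reader might compare the extra cases with COMBI-AD, where 3 of 435 had a combined elevation (3/435 × 556 = 3.8). That is no denominator for true cases: no ALP condition is given, and protocol 1.1.1.6 reports that confounders ruled out drug-induced liver injury in all three.
- A reader might infer that the liver conclusion would change. Nothing in the documents makes it depend on this count.

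**Conclusion.** The point holds as a mismatch between the SAP's table definition and the protocol's own rule. With normal baseline ALT/AST and stable TBL above 2 × ULN, a transaminase rise alone puts a subject in the combined row, and in the potential Hy's law row if ALP is below 2 × ULN. Protocol 6.5.2.1 would not flag that subject.

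This follows from the text and needs no assumption. The number affected does rest on assumption: about 0 to 2.5 of 556, and quite possibly none. The primary endpoint is untouched. The correction is worth making because the difference is undeclared, concerns a named liver-safety definition, and is cheap to remove.

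**What to change.** In SAP 5.8.3, align the baseline rule with protocol 6.5.2.1:
- For subjects with baseline TBL above ULN, require TBL above 2 × baseline and above 2 × ULN in both combined rows.
- For these subjects use the protocol's transaminase limb, which keeps the 3 × ULN floor, and not the SAP's 3 × baseline limb.
- Keep the plain ULN-based rows as a labelled screening version.
- If the different trigger is intended, state so with the reason.

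This changes a table derivation and no clinical follow-up rule. All the laboratory values are already collected (protocol Table 8-7), so the cost is SAP wording and one derivation. The downside is two versions of the combined row to explain. Because the final analysis re-runs the primary-analysis outputs, the change should also be recorded in SAP section 3.

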## 5.8.4 Other safety data

### 5.8.4.1 Electrocardiogram (ECG) and cardiac imaging data

Single standard 12-lead ECGs will be obtained using an ECG machine that automatically calculates heart rate (HR) and measures RR, PR, QRS, QT, and QTcF intervals. All ECG assessments will be performed in the supine position. All ECG assessments will be read and interpreted locally.

ECHO/MUGAs will be performed to assess cardiac ejection fraction. The same procedure (either ECHO or MUGA) should be performed at baseline and follow-up visits. All ECHO/MUGA assessments will be read and interpreted locally.

### Data handling

In case of ECG replicates at any assessment, the average of the ECG parameters at that assessment should be used in the analyses.

### Data analysis

The number and percentage of subjects with notable ECG values will be presented.

- QT, QTcF
  - New value of > 450 and ≤ 480 ms
  - New value of > 480 and ≤ 500 ms
  - New value of > 500 ms
  - Increase from Baseline of > 30 ms to ≤ 60ms
  - Increase from Baseline of > 60 ms

- HR
  - Increase from baseline >25% and to a value > 100 bpm
  - Decrease from baseline >25% and to a value < 50 bpm
- PR
  - Increase from baseline >25% and to a value > 200 ms
  - New value of > 200 ms
- QRS
  - Increase from baseline >25% and to a value > 120 ms
  - New values of QRS > 120 ms

The summaries will include all ECG assessments performed no later than 30 days after the last study treatment date.

A listing of all ECG assessments will be produced and notable values will be flagged. In the listing, the assessments collected during the post-treatment period will be flagged.

For each of the ECG parameters, descriptive statistics at baseline, at each post-baseline time point and changes from baseline at each post-baseline time point will be summarized.

Patients with notable ECG interval values will be listed and the corresponding notable values and abnormality findings will be included in the listings.

Unscheduled ECG measurements will not be used in computing the descriptive statistics for change from baseline at each post-baseline time point. However, they will be used in the analysis of notable ECG values.

For left ventricular ejection fraction (LVEF), descriptive statistics at baseline, at each postbaseline time point and changes from baseline at each post-baseline time point will be summarized. Only the post-baseline assessments that used the same method (ECHO or MUGA) as the baseline assessments will be used to derive the change from baseline

To identify LVEF values of potential clinical importance, the following table will be used to assign categories that align with the grades for ‘Ejection fraction decreased’.

LVEF Parameter Potential Clinical Importance (PCI) Range Unit	Potential Clinical Importance (PCI) Range	Unit
Absolute change from baseline LVEF	
 
• No change or any increase
 
• Any decrease               
 
• >0-<10 decrease
 
• 10-19 decrease
 
• >=20 decrease
 
• >=10 decrease and >= LLN
 
 
 
	%

	
 
• <math>\geq 10</math> decrease and <math>< LLN</math>
 
• <math>> 10</math> decrease and <math>< LLN</math>
 
• <math>\geq 20</math> decrease and <math>\geq LLN</math>
 
• <math>\circ \geq 20</math> decrease and <math>< LLN</math>
 
	
--	--	--

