Grade 2 intolerable or Grade 3	
 Monitor closely Provide supportive care according to institutional standards 	
1st or 2nd occurrence:
 
 Interrupt dabrafenib and trametinib until toxicity recovers to ≤ Grade 1 or baseline. Restart dabrafenib and trametinib at the same dose. 
3rd occurrence:
 
 Restart dabrafenib and trametinib at the next lower dose per Table 6-5. Re-escalation of the subject's dose is recommended if criteria in Section 6.5.1.2 are met 
4th occurrence:
 
 Permanently discontinue dabrafenib and trametinib.
Grade 4	
Monitor closely
 
Provide supportive care according to institutional standards
	
1st occurrence:
 
 Interrupt dabrafenib and trametinib. Dabrafenib and trametinib may be reinitiated at the next lower dose per Table 6-5. Re-escalation of the subject's dose is recommended if criteria in Section 6.5.1.2 are met 
2nd occurrence:
 
 Permanently discontinue dabrafenib and trametinib.

6.5.1.3.11 Mandatory dose modification and management guideline for changes in LVEF suspected to be related to dabrafenib and/or trametinib treatment

Decreases of left-ventricular-ejection-fraction (LVEF) have been observed in patients receiving trametinib in combination with dabrafenib. Therefore, ECHOs must be performed to assess cardiac ejection fraction in regular intervals as outlined in the Visit Evaluation Schedule ([Table 8-1](#)). Dose modification guidance and stopping criteria for LVEF decrease are provided in [Table 6-15](#).

Table 6-15 Mandatory dose modification and recommended clinical management for changes in LVEF suspected to be related to dabrafenib and/or trametinib treatment

Left Ventricular Ejection Fraction decrease (NCI-CTCAE v4.03)		
LVEF-drop (%) & clinical symptoms	Recommended adverse event management guidelines	Mandatory dose modification requirements

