Asymptomatic: Absolute decrease of >10% in LVEF compared to baseline and ejection fraction below the institution's LLN	
 Report as SAE. Closely monitoring LVEF via ECHO, repeat ECHO within 2 weeks*. If the LVEF recovers within 4 weeks (defined as LVEF \geqLLN and absolute decrease \leq10% compared to baseline) 
 Repeat ECHO 2, 4, 8 and 12 weeks after re-start; continue in intervals of 12 weeks thereafter. If repeat LVEF does not recover within 4 weeks. 
 Consult with cardiologist Repeat ECHO after 2, 4, 8, 12, and 16 weeks or until resolution 	
 Interrupt trametinib. If the LVEF recovers, restart trametinib reduced by one dose level per Table 6-5. More than two occurrence, permanently discontinue trametinib. Permanently discontinue trametinib if repeat LVEF does not recover within 4 weeks.
Symptomatic: Resting LVEF 39-20% or >20% absolute reduction from baseline resting LVEF <20%	
 Report as SAE. Consult with cardiologist. Repeat ECHO after 2, 4, 8, 12, and 16 weeks or until resolution. 	
 Permanently discontinue trametinib. Interrupt dabrafenib Restart dabrafenib if LVEF recovers including resolution of symptoms.

* If ECHO does not show LVEF recovery after 2 weeks, repeat ECHO 2 weeks later.

6.5.1.3.12 Mandatory dose modification and management guideline for hypertension suspected to be related to dabrafenib and/or trametinib treatment

Increases in blood pressure have been observed in patients receiving trametinib. For adequate monitoring and management of hypertension, all blood pressure assessments should be performed under the following optimal conditions:

- the subject has been seated with back support, ensuring that legs are uncrossed and flat on the floor
- the subject is relaxed comfortably for at least 5 minutes
- restrictive clothing has been removed from the cuff area and the right cuff size has been selected
- the subject's arm is supported so that the middle of the cuff is at heart level
- the subject remains quiet during the measurement.

In subjects with an initial blood pressure reading within the hypertensive range, a second reading should be taken at least 1 minute later, with the 2 readings averaged to obtain a final blood pressure measurement. The averaged value should be recorded in the eCRF.

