**Table 2-6 Adverse events of special interest by study treatment**

	trametinib	dabrafenib	dabrafenib and trametinib combination
Hepatic disorders	x		x
Pneumonitis/Interstitial lung disease	x		x
Skin toxicities (e.g., rash, dermatitis acneiform)	x		x
Bleeding events	x		x
Hypersensitivity	x	x	x
Pancreatitis		x	x
Neutropenia			x
Pulmonary embolism, deep vein thrombosis	x		x
Pre-renal and intrinsic renal failure		x	x
New primary melanoma		x	x
Non-Cutaneous Treatment-Emergent Malignancies		x	x
Hyperglycemia		x	x
Cardiac related events	x		x
Complicated pyrexia and/or Grade 3 and Grade 4 pyrexia		x	x
Uveitis		x	x
Ocular events (e.g., retinal vein occlusion, retinal pigment epithelial detachment and uveitis)	x		x
Cutaneous squamous cell carcinoma including keratocanthoma		x	x
Hypertension	x		x

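### The SAP's LVEF table is said to align with the ejection-fraction grades but has no row for a low resting LVEF, so a measured fall to 20–39% by under 20 points cannot be counted separately

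*SAP*

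**What the plan says.** SAP 5.8.4.1 (*Data analysis*) states that "the following table will be used to assign categories that align with the grades for" *Ejection fraction decreased*. The parameter tabulated is "Absolute change from baseline LVEF". The ten rows are: no change or any increase; any decrease; >0 to <10; "10-19 decrease"; ≥20; ≥10 and at or above LLN; ≥10 and below LLN; >10 and below LLN; ≥20 and at or above LLN; ≥20 and below LLN. The derivation of change is restricted: "Only the post-baseline assessments that used the same method (ECHO or MUGA) as the baseline assessments" are used.

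Protocol Table 6-15 (section 6.5.1.3.11) is headed "Left Ventricular Ejection Fraction decrease (NCI-CTCAE v4.03". Its row for symptomatic subjects reads "Resting LVEF 39-20% or >20% absolute reduction from baseline resting LVEF <20" per cent. Its row for asymptomatic subjects requires an absolute decrease of more than 10% together with an ejection fraction below the institution's LLN.

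Inclusion criterion 7 (Protocol 5.1) requires baseline LVEF at or above the institutional LLN. Neither document gives a number for LLN.

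**The concern.** A table presented as aligned with the grades should let a reader count subjects who meet the criteria behind them. The only LVEF criterion in the documents under a CTCAE heading has a limb based on the attained resting value, joined by *or* to the limb based on change. The SAP table carries only the change limb. A subject who starts close to LLN can reach a low resting LVEF through a moderate-sized drop, and the table then groups that subject with others whose LVEF remains well above 39%.

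The parameter is of interest in this trial. The protocol's account of COMBI-AD (1.1.1.6) lists decreased ejection fraction among the most common serious adverse events. SAP 5.8.1.2 includes "Cardiac related events" among the adverse events of special interest. Protocol Table 8-1 schedules ECHO/MUGA at screening, Month 1 or 2, Months 6, 9 and 12, and end of treatment. This table is the only categorical summary of measured LVEF that SAP 5.8.4.1 specifies.

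**Working it through.** The plan states no figure to reproduce. The check is whether the gap can be reached under the plan's own rows.

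**Inputs.** The rows come from SAP 5.8.4.1, the resting band of 20–39% from Protocol Table 6-15, and the rule baseline ≥ LLN from Protocol 5.1. LLN is an assumption, taken as 45, 50 and 55% to show the range.

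**Condition.** Let b be baseline and v the post-baseline value, in whole numbers. The subject is in the resting band but outside every ≥20 row when 20 ≤ v ≤ 39 and b − v < 20, so v runs from b − 19 to 39. For each b that gives 39 − (b − 19) + 1 = 59 − b values, so b can be at most 58.

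| Assumed LLN | Baselines | Drops (points) | Whole-number (b, v) pairs |
|---|---|---|---|
| 45% | 45–58% | 6–19 | 14 + 13 + … + 1 = 105 |
| 50% | 50–58% | 11–19 | 9 + 8 + … + 1 = 45 |
| 55% | 55–58% | 16–19 | 4 + 3 + 2 + 1 = 10 |

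These are counts of possible pairs, not of subjects.

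**Where such subjects are tabulated.** With LLN at 50% or 55%, every pair falls in the same four rows: any decrease; 10–19; ≥10 and below LLN; >10 and below LLN. With LLN at 45%, some fall lower. For example, 45% to 39% is a drop of 6 and appears only in any decrease and >0 to <10.

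**Comparison at LLN 50%.**
- 52% to 38%: drop 14, resting value inside 20–39%.
- 60% to 45%: drop 15, resting value outside 20–39%.

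Both subjects fall in the same four rows, so the table cannot tell them apart. The rows that use LLN do not help, because LLN is above the 20–39% band in each scenario.

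**Related edges in the same table.**
- If decimals are recorded, 65% to 45.5% is a drop of 19.5, which fits neither 10–19 nor ≥20.
- The SAP's upper band is ≥20, whereas Table 6-15 uses >20%. From 59% to 39% is a drop of exactly 20, which is in the SAP's top change band but does not meet >20%.
- The rows for ≥10 and below LLN and for >10 and below LLN differ only at a drop of exactly 10.
- Because every decrease row needs a same-method change, a low reading taken after a switch between ECHO and MUGA enters no decrease row.

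**The case against.** The case for leaving the table alone has real force.

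- **Table 6-15 is a dose-modification table, and the SAP does not cite it.** Neither document reproduces the CTCAE v4.03 definitions, so full conformity of the bands cannot be judged from the file. This stands. It limits the point to an incomplete alignment against the one CTCAE-headed criterion that the documents give.
- **The resting band sits in the row for symptomatic subjects.** A reader might infer that a fall from 52% to 36% is severe under Table 6-15 and is reported by the SAP as moderate. The documents do not support that. Without symptoms, such a subject fits the asymptomatic row (with LLN at 50%), and the SAP has a row for exactly that condition (>10 and below LLN). Neither the SAP's LVEF rows nor those of Table 6-15 carry the labels moderate or severe.
- **The table does not rest on change alone.** Five rows also test LLN. This is correct, but none of the five isolates 20–39%.
- **Low values can appear elsewhere.** Adverse events are graded by CTCAE v4.03 and tabulated (SAP 5.8.1, 5.8.1.2). Both rows of Table 6-15 call for SAE reporting. LVEF has descriptive statistics at each time point, which by SAP convention include the minimum. SAP 5.1.1 lists all safety data. This stands as partial cover, but none of it yields a count of subjects with a low measured resting value.
- **Same-method change is sound practice.** Both documents ask for one method throughout, and the restriction applies only to change. This also stands. The restriction should be kept for the change rows, and it gives no reason to leave out resting-value rows.

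**Conclusion.** The point holds as a limited one. The statement that the categories align with the grades is not borne out, because no row uses resting LVEF. A measured fall to 20–39% by under 20 points cannot be counted separately. With LLN assumed at 50% this can arise from baselines of 50–58%. At 45% the range is 45–58%, and at 55% it is 55–58%. The number of subjects affected is unknown because the documents do not give the baseline distribution.

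A reader might also infer that the two limbs coincide from a baseline of 59% upward. They do not: 59% to 39% meets the resting band without exceeding 20 points, and 65% to 44% exceeds 20 points (a drop of 21) while staying outside the band. What is true is narrower. From 59% upward, in whole numbers, anyone reaching 39% or below is already in the SAP's ≥20 row.

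The effect is confined to this descriptive safety table. The primary endpoint and its decision rule are untouched, and the cover from other safety outputs keeps the consequence modest.

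**What to change.** In the LVEF table of SAP 5.8.4.1:

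1. Add rows for worst on-treatment resting LVEF of 20–39% and below 20%. Use all readings whatever the method, with a footnote on method. State how decimal readings are assigned.
2. Keep the same-method restriction for the change rows.
3. Make the change bands contiguous so that a drop between 19 and 20 points has a place.
4. Reconcile the SAP's ≥20 with the protocol's >20%.
5. Do not describe the new rows as matching the symptomatic row of Table 6-15, since the table does not take symptoms into account.

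If the rows are not added, remove the wording that the categories align with the grades.

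The cost is a short SAP edit and a few programmed rows on LVEF values already collected. The downside is some cross-method noise in the resting-value rows, which the footnote discloses. No dose or management rule changes.
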